#### 11.1 Response Evaluation Criteria in Solid Tumors (RECIST) Version 1.1 Guidelines

#### 11.1.1 Categorizing Lesions at Baseline

#### **Measurable Lesions**

- Lesions that can be accurately measured in at least one dimension.
- Lesions with longest diameter twice the slice thickness and at least 10mm or greater when assessed by CT or MRI (slice thickness 5-8mm).
- Lesions with longest diameter at least 20mm when assessed by Chest X-ray.
- Superficial lesions with longest diameter 10mm or greater when assessed by caliper.
- Malignant lymph nodes with the short axis 15mm or greater when assessed by CT.

Note: The shortest axis is used as the diameter for malignant lymph nodes, longest axis for all other measurable lesions.

Note: Tumor lesions that are situated in a previously irradiated area will be considered measurable if there has been progression of disease at that site since radiation occurred.

#### Normal sites

- Cystic lesions: Simple cysts should not be considered as malignant lesions and should not be recorded either as target or non-target disease. Cystic lesions thought to represent cystic metastases can be measurable lesions, if they meet the specific definition above.
- If non-cystic lesions are also present, these are preferred as target lesions.
- Normal nodes: Nodes with short axis <10mm are considered normal and should not be recorded or followed either as measurable or non-measurable disease.

#### 11.1.2 Recording Tumor Assessments

All sites of disease must be assessed at baseline. Baseline assessments should be done as close as possible prior to study start. For an adequate baseline assessment, all required scans must be done within 28 days prior to treatment and all disease must be documented appropriately. If baseline assessment is inadequate, subsequent statuses generally should be indeterminate.

#### **Target lesions**

All measurable lesions up to a maximum of 2 lesions per organ, 5 lesions in total, representative of all involved organs, should be identified as target lesions at baseline. Target lesions should be selected on the basis of size (longest lesions) and suitability for accurate repeated measurements.

Record the longest diameter for each lesion, except in the case of pathological lymph nodes for which the short axis should be recorded. The sum of the diameters (longest for non-nodal lesions, short axis for nodal lesions) for all target lesions at baseline will be the basis for comparison to assessments performed on study. If two target lesions coalesce, the measurement of the coalesced mass is used. If a large target lesion splits, the sum of the parts is used. Measurements for target lesions that become small should continue to be recorded. If a target lesion becomes too small to measure, 0mm should be recorded if the lesion is considered to have disappeared; otherwise a default value of 5mm should be recorded.

Note: When nodal lesions decrease to <10mm (normal), the actual measurement should still be recorded.

#### Non-target disease

All non-measurable disease is non-target. All measurable lesions not identified as target lesions are also included as non-target disease. Measurements are not required but rather assessments will be expressed as ABSENT, INDETERMINATE, PRESENT/NOT INCREASED, INCREASED. Multiple non-target lesions in one organ may be recorded as a single item on the case report form (eg, 'multiple enlarged pelvic lymph nodes' or 'multiple liver metastases').

11.1.3 Objective Response Status at Each Evaluation

Disease sites must be assessed using the same technique as baseline, including consistent administration of contrast and timing of scanning. If a change needs to be made the case must be discussed with the radiologist to determine if substitution is possible. If not, subsequent objective statuses are indeterminate.

#### Target disease

- Complete Response (CR): Complete disappearance of all target lesions with the exception of nodal disease. All target nodes must decrease to normal size (short axis <10mm). All target lesions must be assessed.
- Partial Response (PR): Greater than or equal to 30% decrease under baseline of the sum of diameters of all target measurable lesions. The short diameter is used in the sum for target nodes, while the longest diameter is used in the sum for all other target lesions. All target lesions must be assessed.
- Stable: Does not qualify for CR, PR or Progression. All target lesions must be assessed. Stable can follow PR only in the rare case that the sum increases by less than 20% from the nadir, but enough that a previously documented 30% decrease no longer holds.
- Objective Progression (PD): 20% increase in the sum of diameters of target measurable lesions above the smallest sum observed (over baseline if no decrease in the sum is observed during therapy), with a minimum absolute increase of 5mm.
- Indeterminate. Progression has not been documented, and
  - One or more target measurable lesions have not been assessed;

• Assessment methods used were inconsistent with those used at baseline;

or

• One or more target lesions cannot be measured accurately (eg, poorly visible unless due to being too small to measure);

or

• One or more target lesions were excised or irradiated and have not reappeared or increased.

#### Non-target disease

- CR: Disappearance of all non-target lesions and normalization of tumor marker levels. All lymph nodes must be 'normal' in size (<10mm short axis).
- Non-CR/Non-PD: Persistence of any non-target lesions and/or tumor marker level above the normal limits.
- PD: Unequivocal progression of pre-existing lesions. Generally the overall tumor burden must increase sufficiently to merit discontinuation of therapy. In the presence of SD or
- PR in target disease, progression due to unequivocal increase in non-target disease should be rare.
- Indeterminate: Progression has not been determined and one or more non-target sites were not assessed or assessment methods were inconsistent with those used at baseline.

#### New Lesions

The appearance of any new unequivocal malignant lesion indicates PD. If a new lesion is equivocal, for example due to its small size, continued assessment will clarify the etiology. If repeat assessments confirm the lesion, then progression should be recorded on the date of the initial assessment. A lesion identified in an area not previously scanned will be considered a new lesion. Supplemental Investigations If CR determination depends on a residual lesion that decreased in size but did not disappear completely, it is recommended the residual lesion be investigated with biopsy or fine needle aspirate. If no disease is identified, objective status is CR. If progression determination depends on a lesion with an increase possibly due to necrosis, the lesion may be investigated with biopsy or fine needle aspirate to clarify status.

#### **Objective/Subjective**

Patients requiring discontinuation of treatment without objective evidence of disease progression should not be reported as PD on tumor assessment CRFs. This should be indicated on the end of treatment CRF as off treatment due to Global Deterioration of Health Status. Every effort should be made to document objective progression even after discontinuation of treatment.

#### For Participants with Measurable Disease (*i.e.*, Target Disease)

#### Table 10: Best Overall Response for Measurable Disease (Target Disease)

	Target	Non-Target	New	Overall	Best Overall Response when
--	--------	------------	-----	---------	----------------------------

NCI Protocol #: N/A DF/HCC Protocol #: 18-602 Protocol Version Date: December 11, 2023

Lesions	Lesions	Lesions	Response	Confirmation is Required*		
CR	CR	No	CR	≥4 wks Confirmation**		
CR	Non-CR/Non-	No	PR			
	PD					
CR	Not evaluated	No	PR	\1 wkg Confirmation**		
PR	Non-CR/Non-	No	PR	24 wks Commutation · · · 		
	PD/not					
	evaluated					
SD	Non-CR/Non-	No	SD	Decumented at least once >4		
	PD/not			bocumented at least once $\geq 4$		
	evaluated			wks from baseline**		
PD	Any	Yes or No	PD			
Any	PD***	Yes or No	PD	no prior SD, PR or CR		
Any	Any	Yes	PD			
* See RE	CIST 1.1 manuscr	ript for further	details on what	is evidence of a new lesion.		
** Only fo	or non-randomized	trials with res	ponse as primar	y endpoint.		
* See KE ** Only fo	or non-randomized	trials with res	ponse as primar	y endpoint.		

\*\*\* In exceptional circumstances, unequivocal progression in non-target lesions may be accepted as disease progression.

Note: Participants with a global deterioration of health status requiring discontinuation of treatment without objective evidence of disease progression at that time should be reported as "*symptomatic deterioration*." Every effort should be made to document the objective progression even after discontinuation of treatment.

#### **Determination of Best Overall Response**

The best overall response is the best response recorded from the start of the treatment until disease progression/recurrence (taking as reference for progressive disease the smallest sum on study). For CR and PR, the patient's best response assignment will depend on the achievement of both measurement and confirmation criteria. CR and PR must be confirmed by 2 measurements at least 4 weeks apart. In the case of SD, follow up measurements must have met the SD criteria at least once after study entry at a minimum interval of 6 weeks.

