### 1.2 **Primary Objectives**

To assess the activity of mirvetuximab soravtansine and pembrolizumab in advanced or recurrent EC as determined by the frequency of patients who are alive and progression-free for a minimum of 6 months (PFS6) after initiating therapy, or who have objective tumor responses by RECIST 1.1 criteria.

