#### 5.4 General Concomitant Medication and Supportive Care Guidelines

All concomitant medications, over-the-counter, herbal supplements and supportive therapy taken within 28 days of Cycle 1, day 1 and through 30 days after last study treatment must be recorded on the appropriate eCRF. The identity of all medications, dosage, and route of administration,

frequency, duration of administration, and indication for use will be recorded in the appropriate sections of the eCRF.

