## 5.7 Criteria for Taking a Participant Off Study

Patients may voluntarily withdraw from the study treatment at any time for any reason, and without prejudice to further treatment. In addition, patients may be withdrawn by the Investigator if they do not feel the patient is deriving clinical benefit or because the patient is experiencing unacceptable toxicity, patient is lost to follow up, or patient is not compliant with study procedures.

Patients who withdraw or are removed from the study treatment will have an off-treatment visit within 7 days of the decision to discontinue study treatment. The final visit will occur at the time the participant discontinues study medication. Following the Final Visit, participants will be followed for disease progression (if reason for treatment discontinuation is other than

progression) and survival, and reassessment for toxicity will be performed up to 30 days after the last treatment dose. Participants will be followed for up to 3 years by phone after removal from study or until death, whichever occurs first. Survival status should be checked every 6 months during that time

The reason for taking a participant off study, and the date the participant was removed, must be documented in the case report form (CRF). In addition, the study team will ensure Off Treatment/Off Study information is updated in OnCore in accordance with DF/HCC policy REGIST-101.

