#### 13.1 Study Design/Endpoints

#### Primary Endpoints

To assess the activity of mirvetuximab soravtasine in combination with pembrolizumab in patients with recurrent or persistent MSS and FR $\alpha$  positive endometrial cancer by evaluating the frequency of patients who survive progression-free for at least 6 months (PFS6) after initiating therapy or have objective tumor response.

Statistical considerations are developed for co-primary objectives to evaluate the objective response rate (ORR) by RECIST 1.1 and rate of progression-free survival at 6 months (PFS6), with a two-stage design that allows for early stopping for futility.

A two-stage test was constructed using the method of Sill, Rubinstein, Litwin and Yothers [36] with the goal of stopping early for futility to limit patient exposure to an inactive agent while restricting the probabilities of type I and type II errors to approximately 10% and 15%, respectively. For the co-primary endpoints, a true ORR of 5% or less and a rate of progressionfree survival at 6 months of (PFS6) 10% or less would not be of clinical interest (H0:  $\pi_{OR} \leq 5\%$ AND  $\pi_{PFS6} \le 10\%$ ), whereas an improvement to a 20% objective response rate or 30% PFS6 rate would warrant further investigation of the study treatment. In the first stage, 16 patients will be enrolled and accrual will pause. If there are at least two objective responses or two patients progression-free at 6 months among the first 16 patients, the second stage of accrual will commence where an additional 19 patients will be enrolled. If at the end of the trial there are at least 4 treated patients with an objective response or 8 patients progression-free at 6 months, the study treatment will be considered worthy of further study. Specifically, analysis of historical data (GOG129 and GOG229 series) based on similar population of patients with endometrial cancer where the levels of activity were believed to be inactive to modestly active shows that an unacceptable rate for objective response ( $\pi_{OR}$ ) is 5% and for PFS6 ( $\pi_{PFS6}$ ) is 10%, respectively. A bivariate test of the co-primary endpoints is constructed as follows:

H0:  $\pi_{OR} \leq 5\%$  AND  $\pi_{PFS6} \leq 10\%$ 

vs. H1:  $\pi_{OR} > 5\%$  OR  $\pi_{PFS6} > 10\%$ 

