#### 13.7.2 Evaluation of the Primary Efficacy Endpoint

All participants included in the study must be assessed for response to treatment, even if there are major protocol treatment deviations or if they are ineligible. Each participant should be assigned one of the following categories: 1) complete response, 2) partial response, 3) stable disease, 4) progressive disease, 5) early death from malignant disease, 6) early death from toxicity, 7) early death because of other cause, or 9) unknown (not assessable, insufficient data). By arbitrary convention, category 9 usually designates the "unknown" status of any type of data in a clinical database.

All participants who have measurable disease present at baseline, have received at least one cycle of therapy, and have had their disease re-evaluated will be considered evaluable for response. Participants in response categories 5-9 will not be considered evaluable but will remain within the intention to treat analysis.

Patients who develop brain metastasis on study, but continue on study after definitive treatment of their cranial disease, will be considered to have had progressive disease at the point of the diagnosis of the initial brain metastasis.

All conclusions should be based on all evaluable participants. Subanalyses may then be performed on the basis of a subset of participants, excluding those for whom major protocol deviations have been identified (e.g., early death due to other reasons, early discontinuation of treatment, major protocol violations, etc.). However, these subanalyses may not serve as the basis for drawing conclusions concerning treatment efficacy, and the reasons for excluding participants from the analysis should be clearly reported. The 95% confidence intervals should also be provided.

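### Neither co-primary endpoint stops at the start of non-protocol anticancer therapy, so progression-free time on a later regimen can count as a PFS6 success of the study combination

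*Combined protocol and SAP*

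**What the plan says.** **Response.** Section 11.1.3 (Determination of Best Overall Response) states: "The best overall response is the best response recorded from the start of the treatment until disease progression/recurrence". CR and PR need confirmation at least 4 weeks apart. The window has no other end point.

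**PFS6.** Section 1.2 counts patients who are "alive and progression-free for a minimum of 6 months (PFS6) after initiating therapy", and Section 13.1 uses the same idea. Sections 13.4 and 13.5 only refer back to 13.1. Section 13.6 names Kaplan-Meier and gives no censoring rule.

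**After stopping.** Under Section 5.7, after the final visit "participants will be followed for disease progression (if reason for treatment discontinuation is other than" progression). Section 11.1.3 also asks that objective progression be sought after discontinuation. Deterioration without objective evidence is not to be recorded as PD.

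**Other treatment.** The prohibited list in Section 5.4.3 applies to the screening and treatment phases. Section 5.4 says that medications taken "within 28 days of Cycle 1, day 1 and through 30 days after last study treatment must be recorded". New anticancer therapy is otherwise mentioned only in the pregnancy and event-reporting windows of Sections 7.6.2, 7.7.3 and 7.7.4.

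**Local treatment.** In Section 11.1.3 a target-disease assessment is Indeterminate if "One or more target lesions were excised or irradiated and have not reappeared or increased". Section 13.7.2 has one specific rule: a patient who develops brain metastases and continues after treatment for them "will be considered to have had progressive disease at the point of the diagnosis of the initial brain metastasis".

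**Analysis set.** Section 13.7.2 rests conclusions on all evaluable participants. It does not let subanalyses that exclude, for example, early discontinuations support efficacy conclusions.

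**The concern.** Patients can leave treatment without progression: Section 5.5 lists unacceptable adverse events and withdrawal, and Table 4 requires permanent discontinuation for some pneumonitis. Such a patient may start another systemic regimen before progressing. If she is then progression-free at 6 months, the written definition makes her a success of the combination.

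The trial has no control arm to offset this, and its decision rests on small counts: 2 responses or 2 PFS6 among 16 to continue, then 4 responses or 8 PFS6 among 35 to declare activity. One reclassified patient can change either decision. Because Section 13.7.2 limits what subanalyses may support, the rule belongs in the endpoint definition and not in a later exclusion.

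**Working it through.** **Inputs from Section 13.1 and Table 12.** The null is "a true ORR of 5% or less" together with PFS6 of 10% or less. The error targets are described as "restricting the probabilities of type I and type II errors to approximately 10% and 15%, respectively". Stop after 16 patients if responses ≤1 and PFS6 ≤1. Reject the null if responses ≥4 or PFS6 ≥8 among 35.

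**Step 1: reproduce the plan (independent endpoints).**
- P(responses ≤1 of 16 at 5%) = 0.95^16 + 16 × 0.05 × 0.95^15 = 0.811.
- P(PFS6 ≤1 of 16 at 10%) = 0.90^16 + 16 × 0.10 × 0.90^15 = 0.515.
- Probability of early termination = 0.811 × 0.515 = 0.417, as printed.
- The exact two-stage sum gives type I error 0.0977 (printed 0.098) and power 0.889 and 0.873, as printed.
- With 90% of null responders also PFS6 successes, early termination is 0.502 and type I error 0.088. The 0.502 matches Table 12's dependence row; its printed alpha of 0.88 is evidently a misprint for 0.088.

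**Step 2: let later therapy affect PFS6 only.** The documents give none of the following, so these are assumptions. Let f be the share of patients who stop without PD and start other systemic therapy before 6 months. Let s be the proportion of switchers, among those who would otherwise have failed PFS6, who are progression-free at 6 months on the new regimen. The combination itself is at the null and ORR stays at 5%.

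Observed PFS6 = 0.10 + f × 0.90 × s. For f = 10% and s = 40% this is 0.10 + 0.10 × 0.90 × 0.40 = 0.136.

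| f | s | PFS6 | Type I error, independence | Type I error, 90% of responders also PFS6 |
|---|---|---|---|---|
| 0 | – | 0.100 | 0.098 | 0.088 |
| 5% | 20% | 0.109 | 0.110 | 0.097 |
| 10% | 20% | 0.118 | 0.125 | 0.109 |
| 15% | 20% | 0.127 | 0.144 | 0.125 |
| 5% | 40% | 0.118 | 0.125 | 0.109 |
| 10% | 40% | 0.136 | 0.168 | 0.145 |
| 15% | 40% | 0.154 | 0.229 | 0.201 |

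The expected number of extra PFS6 successes among 35 runs from 35 × 0.009 = 0.3 to 35 × 0.054 = 1.9. Early stopping also weakens: at f = 10% and s = 40%, under independence, early termination falls from 0.417 to 0.275.

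**Step 3: upper scenario.** Suppose every off-study response were also scanned and confirmed, with 15% of switchers responding: ORR = 0.05 + f × 0.95 × 0.15. With s = 40%, type I error at f = 5%, 10% and 15% is 0.160, 0.241 and 0.339 under independence, and 0.138, 0.203 and 0.281 with 90% overlap.

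**The case against.** **Off-study responses are unlikely to be captured.** A reader might take the Step 3 figures as the size of the problem. Section 5.5.1 schedules scans every 2 cycles, on suspected progression and at withdrawal, and the Study Calendar has no tumour measurement in the off-treatment column. A confirmed response needs two assessments that nobody has scheduled. This stands: the main route is PFS6, and Step 3 is an upper scenario only.

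**The inputs are generous.** An s of 40% exceeds the trial's own PFS6 target of 30%. Switchers would already have had one to four chemotherapy lines plus the combination. The switching rate has no source. This also stands, so the 20% rows matter as much as the 40% rows.

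**The null may share the rule.** The 5% and 10% rates come from the GOG129 and GOG229 series. The documents do not say whether those series counted time on later therapy. If they did, trial and null are on the same footing, and counting switchers as failures would make the test conservative. Inflation is therefore conditional.

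**Local treatment.** It is tempting to infer that excising or irradiating a lesion can create a response. It cannot: CR and PR require all target lesions to be assessed, and such a lesion makes the status Indeterminate. What remains is narrower. Indeterminate is not PD, and the plan does not say how it counts for PFS6. The brain-metastasis rule only dates progression.

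**Later therapy is partly visible.** A reader might conclude that it could never be identified. Medications are recorded to 30 days after the last dose, which would show early switches, and the safety windows that depend on new anticancer therapy require sites to know of it. Later starts may still be missed.

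**Counting outcomes regardless of later therapy is a recognised approach.** True, but the plan does not state that choice, and in a single-arm activity screen it credits another regimen to the combination.

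**Conclusion.** The gap is real and lies in both co-primary definitions: neither ends at non-protocol anticancer therapy, and follow-up for progression continues after stopping. Patients who progress before switching are unaffected. The practical effect is mainly on PFS6, through systemic therapy started before progression and before 6 months.

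Its frequency is unknown. With 5% to 15% switching, only PFS6 affected and independent endpoints, type I error moves from 0.098 to about 0.11–0.14 (s = 20%) or 0.12–0.23 (s = 40%). It is somewhat lower under dependence and higher if off-study responses are also captured. These figures are illustrations, conditional on the historical rates not having counted time on later therapy. The missing clause is certain; the amount of inflation is not. The change is worth making because it is cheap and the decision counts are small.

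**What to change.** 1. In Section 11.1.3, end the best-overall-response window at progression or the first non-protocol anticancer therapy, whichever is earlier.
2. In Sections 13.1 and 13.5, do not count as a PFS6 success a patient who starts such therapy before 6 months, or whose 6-month status is Indeterminate because a target lesion was irradiated or excised. Report the regardless-of-therapy result as a sensitivity analysis.
3. In Section 13.6, state one handling of new therapy for Kaplan-Meier PFS that agrees with the PFS6 rule, and show the alternative as sensitivity. Censoring at the switch while counting the same patient as a PFS6 failure would give two different 6-month rates, and censoring after a toxicity stop may be informative.
4. Record the date and type of first subsequent anticancer therapy at the off-treatment visit and at the 6-monthly phone contacts already planned.
5. State whether the historical 5% and 10% rates counted time on later therapy, so that null and endpoint follow the same rule.

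The cost is a few sentences and a small CRF addition. Sample size and decision thresholds do not change. The downside is that ORR and PFS6 may be slightly lower.
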